### **3.8. Number of Sites**

Approximately 8 sites located in the US will be included in this trial. Additional sites may be included based on enrollment and study timelines.

### **3.9. Estimated Study Duration**

It is anticipated that this study will take approximately 42 months to complete.

Patient participation will include screening, treatment, and follow-up. Screening will last up to 30 days before first dose of study drugs, during which time the patient's eligibility and baseline characteristics will be determined. Treatment with study drugs may be continued until an unacceptable drug-related toxicity occurs, patient refusal, or until disease progression. Post treatment, patients will be observed for disease progression and survival until death, withdrawal of consent, or the end of the study, whichever occurs first.

Recruitment will cease when one of the following occurs:

- Study treatment is considered too toxic to continue treatment before the anticipated number of patients are recruited. This assessment will be made by the CTSC.
- The stated number of patients to be recruited is reached. This number may be increased to include replacement patients for those who are not DLT evaluable or patients in Phase 2 who are not evaluable for efficacy as defined in [Section 11](#); and patients added to intermediate dose or expanded cohorts as determined by the CTSC, and approved, if necessary, by the appropriate IRBs.

- The stated objectives of the trial are achieved.

Interim study database lock may be implemented at the discretion of the CTSC once all Phase 2 patients enrolled have achieved at least 1 tumor efficacy assessment.

## 4. SUBJECT SELECTION AND ENROLLMENT

### 4.1. Inclusion Criteria

1. Adults  $\geq$  18 years old.

2. Histological Diagnosis

a. Phase 1b only:

Histologically or cytologically confirmed advanced solid malignancy with an emphasis on CRC, head and neck, breast, pancreatic and ovarian cancers who have been treated with at least one regimen of prior systemic therapy, or who refuse systemic therapy, and for which there is no curative therapy available.

b. Phase 2:

- KRAS Mutant CRC: Histologically confirmed advanced KRAS mutant CRC who have progressed or are ineligible for fluoropyrimidine, irinotecan- and oxaliplatin-based chemotherapy

OR

- KRAS Wild-Type CRC: Histologically confirmed advanced KRAS wild-type CRC who have progressed or are ineligible for fluoropyrimidine, irinotecan- and oxaliplatin-based chemotherapy and who are refractory to at least 1 prior systemic therapy that included an anti-EGFR antibody, such as cetuximab, panitumumab, or others.

Patients should have disease progression during prior anti-EGFR therapy or within 6 months of the last day of treatment with the anti-EGFR.

3. Eastern Cooperative Oncology Group (ECOG) Score 0-2.

4. For the Phase 2 part only: Disease that is measurable or assessable for response according to RECIST Version 1.1 Criteria.

5. Laboratory measurements, blood counts:

- Hemoglobin  $\geq$  9.5 g/dL.
- Absolute neutrophil count (ANC)  $\geq 1.0 \times 10^9/\text{mL}$ .

- Platelets  $\geq 75 \times 10^9/\text{mL}$ .
6. Laboratory measurements, hepatic function:
- Aspartate aminotransferase (AST)/alanine aminotransferase (ALT)  $< 5 \times$  upper limit of normal (ULN).
  - Bilirubin  $< 1.5 \times \text{ULN}$  or  $3.0 \times \text{ULN}$  and primarily unconjugated if patient has a documented history of Gilbert's syndrome or a genetic equivalent.
7. Laboratory measurements, renal function:
- Serum creatinine  $\leq 1.5 \times \text{ULN}$  or, if elevated, a calculated glomerular filtration rate (GFR  $> 30 \text{ mL/min}/1.73 \text{ m}^2$ ).
8. Negative urine or serum pregnancy test within 30 days before administration of Hu5F9-G4 for women of childbearing potential.
9. Females of childbearing potential must be willing to use 1 effective method of contraception during the study and continue for 4 months after the last dose of Hu5F9-G4 and 6 months after the last dose of cetuximab.
10. Males must be willing to use 1 effective method of contraception and refrain from sperm donation during the study and continue for 4 months after the last dose of Hu5F9-G4 and 6 months after the last dose of cetuximab, if the partner is a female of childbearing potential.
11. Subject has provided informed consent.
12. Must be willing and able to comply with the clinic visits and procedures outlined in the study protocol.
13. Phase 2 only:
- Willing to consent to 1 mandatory pre-treatment and 1 on-treatment tumor biopsy, unless determined to not be feasible by the Investigator (reasons include, but are not limited to, lack of accessible tumor tissue to biopsy and patient safety issues).

#### 4.2. Exclusion Criteria

1. Patients with active brain metastases (patients with stable treated central nervous system [CNS] lesions who are off corticosteroid and radiation therapy for at least 3 weeks are not considered active).
2. Prior anti-cancer therapy including chemotherapy, hormonal therapy, or investigational agents within 2 weeks or within at least 4 half-lives prior to Hu5F9-G4 dosing (up to a maximum of 4 weeks), whichever is longer. In all situations, the maximum required washout period will not exceed 4 weeks prior to the day of first treatment with Hu5F9-G4. Localized non-CNS radiotherapy, previous hormonal therapy with luteinizing hormone releasing hormone (LHRH) agonists for prostate cancer, low-dose steroids (oral prednisone or equivalent  $\leq$  20 mg per day), and treatment with bisphosphonates and RANKL inhibitors are not criteria for exclusion.
3. Prior treatment with CD47 or SIRPa-targeting agents.
4. Known active or chronic hepatitis B or C infection or human immunodeficiency virus (HIV).
5. RBC transfusion dependence, defined as requiring more than 2 units of RBC transfusions during the 4-week period prior to Screening. RBC transfusions are permitted during the Screening period and prior to enrollment to meet the hemoglobin inclusion criteria.
6. History of hemolytic anemia or Evans syndrome in the last 3 months.
7. Phase 2 only:  
Second malignancy, except treated basal cell or localized squamous skin carcinomas, localized prostate cancer, or other malignancy for which treatment was completed at least 3 years ago and for which there is no evidence of recurrence.
8. Hypersensitivity to the active substance or to murine proteins, or to any of the other excipients of cetuximab listed in [Appendix A](#).
9. Significant medical diseases or conditions, as assessed by the Investigators and Sponsor, that would substantially increase the risk-benefit ratio of participating in the study. This includes, but is not limited to, acute myocardial

- infarction within the last 6 months, unstable angina, uncontrolled diabetes mellitus, significant active infections, severely immunocompromised state, and congestive heart failure New York Heart Association (NYHA) Class II-IV.
10. History of psychiatric illness or substance abuse likely to interfere with ability to comply with protocol requirements or give informed consent.
  11. Pregnancy or active breast feeding.
  12. Positive IgG component of the direct antiglobulin test (DAT).

#### **4.3. Patient Screening**

All patients who enter the Screening period for the study, which starts when the patient signs the informed consent form, receive a unique subject identification number before any study procedures are performed. This number is used to identify the patient throughout the clinical trial and must be used on all study documentation related to that patient, including if a patient is rescreened.

Patient Screening laboratory assessments may be tested repeatedly within the 30 days prior to the first dose of study treatment. Patients who screen fail may undergo repeated screening if the patient's medical condition has changed.

All patients who provide informed consent must be registered in the electronic data capture (EDC) system, including any screen failures.

A patient is defined as enrolled in the study once all eligibility criteria have been satisfied and the Sponsor or designee has confirmed the cohort or study arm assignment. After signing the informed consent, eligible patients are expected to receive the first dose of Hu5F9-G4 (Study Day 1) within 30 days.

#### **4.4. Informed Consent Process**

All participants must be provided a consent form describing the study with sufficient information for participants to make an informed decision regarding their participation. Participants must sign the Institutional Review Board/Research Ethics Committee (IRB/REC) approved informed consent form (ICF) prior to participation in any study specific procedure. Data from assessments performed as part of standard

of care prior to ICF signature may be used if they are within the required Screening period. The participant must receive a copy of the signed and dated consent documents. A signed copy (in paper or electronic format) of the consent documents must be retained in the medical record or research file.

#### **4.5. Registration Process**

Patient will be assigned the subject number at the time of consent. The site will register the patient through interactive web response technology (IWRS) with the Sponsor or representative within 2 days of consent.

Prior to being assigned a dose cohort or treatment arm, patients must have signed the informed consent and satisfied all of the eligibility criteria. Once patients have been assigned to a dose cohort or treatment arm, they will be considered enrolled. The Investigator will determine the eligibility of the patient.

## **5. STUDY DRUG INFORMATION**

See the Pharmacy Manual for detailed instructions for Hu5F9-G4 and cetuximab preparation and handling.

### **5.1. Hu5F9-G4**

#### **5.1.1. Physical Description of Study Drug**

The active pharmaceutical ingredient (API) is Hu5F9-G4, a humanized IgG4 monoclonal antibody of the IgG4 kappa isotype containing a Ser-Pro (S-P) substitution in the hinge region (position 228) of the heavy chain to reduce Fab arm exchange. It comprises a disulfide-linked glycosylated tetramer, consisting of two identical 444 amino acid heavy gamma chains and two identical 219 amino acid kappa light chains. Hu5F9-G4 targets the human CD47 antigen. Hu5F9-G4 drug product is a sterile, clear, colorless, preservative-free liquid intended for intravenous (IV) infusion.

Hu5F9-G4 active pharmaceutical ingredient (API) is manufactured under current Good Manufacturing Practices.

Hu5F9-G4 is supplied in single-use, 10-mL vials containing 200 mg of the antibody in a formulation of 10 mM sodium acetate, 5% (w/v) sorbitol, 0.01% (w/v) polysorbate 20, at pH of 5.0.

The labeling complies with the requirements of the applicable regulatory agencies.

Additional details about Hu5F9-G4 are provided in the Pharmacy Manual.

### **5.2. Cetuximab**

#### **5.2.1. Physical Description of Study Drug**

Erbitux® (cetuximab) is a recombinant, human/mouse chimeric monoclonal antibody that binds specifically to the extracellular domain of the human epidermal growth factor receptor (EGFR). Cetuximab is composed of the Fv regions of a mouse anti-EGFR antibody with human IgG1 heavy and kappa light chain constant regions

and has an approximate molecular weight of 152 kDa. Cetuximab is produced in mammalian (murine myeloma) cell culture.

Cetuximab is a sterile, clear, colorless liquid of pH 7.0 to 7.4, which may contain a small amount of easily visible, white, amorphous cetuximab particulates. Cetuximab is supplied at a concentration of 2 mg/mL as a 100 mg/50 mL single-use vial (NDC 66733 948 23), or as a 200 mg/100 mL single-use vial (NDC 66733 958 23) as a sterile, injectable liquid containing no preservatives individually packaged in a carton. Cetuximab is formulated in a solution containing 8.48 mg/mL sodium chloride, 1.88 mg/mL sodium phosphate dibasic heptahydrate, 0.41 mg/mL sodium phosphate monobasic monohydrate, and Water for Injection, USP ([Appendix A](#)).

Store vials under refrigeration at 2°C to 8°C (36°F to 46°F) and do not freeze. Increased particulate formation may occur at temperatures at or below 0°C. Preparations of cetuximab in infusion containers are chemically and physically stable for up to 12 hours at 2°C to 8°C (36°F to 46°F) and up to 8 hours at controlled room temperature (20°C to 25°C; 68°F to 77°F). Discard any remaining solution in the infusion container after 8 hours at controlled room temperature or after 12 hours at 2°C to 8°C. Discard any unused portion of the vial.

## 6. TREATMENT PLAN

### 6.1. Study Drug Administration Guidance: Hu5F9-G4 and Cetuximab

#### 6.1.1. Dosing

Planned Phase 1b dose levels are presented in [Table 1](#) and the Phase 2 dose and schedule is presented in [Table 2](#).

The dose of each study drug will be calculated based on actual weight at enrollment (using weight obtained either at Screening or on Day 1) and remains constant throughout the study, unless there is a > 10% change in weight from baseline. Modifications to the study drug doses administered should be made for a > 10% change in body weight and for dose modifications as described in [Section 6.1.4](#). Dose modifications for changes in body weight < 10% may be made according to local institutional guidelines.

All patients will receive an Hu5F9-G4 priming dose of 1 mg/kg on Day 1.

The duration of the infusion of the priming dose will be 3 hours ( $\pm$  30 minutes).

The priming dose will be followed by a weekly maintenance dose. The duration of the infusion of the maintenance dose will be 2 hours ( $\pm$  30 minutes). The first maintenance dose will be administered starting on Day 8 after the completion of the first dose of cetuximab. All subsequent maintenance doses of Hu5F9-G4 will be administered at the start of each study week ( $\pm$  1 day). Hu5F9-G4 will be administered at least 1 hour after the completion of cetuximab administration.

All patients should be monitored for at least 1 hour post-infusion for the first 4 weeks.

Post-infusion monitoring should begin after the last study drug is given.

Post-infusion monitoring is not required for doses after Cycle 1. Patients who experience any treatment-related AEs during the observation period should be further monitored, as clinically appropriate.

Patients will receive a cetuximab dose of 300-400 mg/m^2 given IV starting on Day 8, followed by weekly dosing at 200-250 mg/m^2 on Days 15 and 22. Starting at

Cycle 2, and for each cycle thereafter, cetuximab will be given weekly starting on Day 1. (Details are provided in [Section 6.1.4.2.](#))

Because of the possibility of an initial increase in tumor burden caused by immune cell infiltration in the setting of a T-cell response (termed pseudoprogression) with immunotherapy treatment, radiographic progression defined as unconfirmed progressive disease according to iRECIST ([Seymour 2017](#)) may not be indicative of true PD. Hu5F9-G4 and cetuximab combination treatment may continue past the initial determination of disease progression according to iRECIST as long as the following criteria are met:

- No new symptoms or worsening of previous symptoms
- Tolerance of Hu5F9-G4 and avelumab
- Stable ECOG performance status
- Treatment beyond progression will not delay an imminent intervention to prevent serious complications of disease progression (for example, central nervous system [CNS] metastases)

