### **3.4. Planned Phase 2 Dose and Schedule**

Based on review of safety, efficacy, and PK data available from Phase 1b, the planned and alternate Phase 2 dose and schedule of Hu5F9-G4 that will be used in the Phase 2 part of this study and is shown in [Table 2](#).

When both study drugs are given on the same visit day, Hu5F9-G4 will be administered at least 1 hour after the completion of the cetuximab administration.

Starting with Cycle 2, the Day 8 and Day 22 dosing of Hu5F9-G4 has been removed, compared with the Phase 1b schedule (i.e., dosing is Q2W). Patients enrolled in the Phase 1b part of the study who have been on study for at least 8 weeks may have their dose revised to the RP2DS, at the discretion of the Investigator.

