#### **6.1.3. Repriming**

The following list describes the requirements for Hu5F9-G4 repriming.

- Patients who experience an interruption of >2 weeks after receiving only the priming dose (1 mg/kg) must be “reprimed” by receiving the Hu5F9-G4 priming dose of 1 mg/kg IV over 3 hours ( $\pm$ 30 minutes) and 3 subsequent weekly maintenance doses prior to starting the Q2W dosing schedule.
- Patients who experience an interruption of >4 weeks after receiving at least 1 maintenance dose (i.e., 30 mg/kg) must be “reprimed” by receiving the Hu5F9-G4 priming dose of 1 mg/kg IV over 3 hours ( $\pm$ 30 minutes) and 3 weekly maintenance doses prior to starting the Q2W schedule.
- Cetuximab must be administered as regularly scheduled (e.g. Hu5F9-G4 repriming doses may be administered on the same day as cetuximab is given and administration of cetuximab once weekly should be maintained.)
- Premedication is required for the repriming dose and the first weekly maintenance dose ([Section 6.1.2](#)).

On the day that patients receive their repriming dose, a predose ADA sample is to be collected.

For patients who are reprimed, the following assessments are to be performed at the supplemental weekly visits (e.g., Day 8, Day 22):

- Complete blood count (CBC) with differential, platelets, reticulocytes

- Peripheral blood smear
- Serum chemistry
- Haptoglobin, D-dimer, thrombin, fibrinogen
- PT/INR, aPTT
- Vital signs
- Physical examination
- Adverse events
- Concomitant medications

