#### **6.1.4.1.2. Maintenance Dose Schedule Modification**

Patients who have completed at least 8 weeks of weekly maintenance therapy may stay at the same infusion dose, but may have their Hu5F9-G4 schedule of administration extended to every 2 or 3 weeks, if supported by PK data and approved by the CTSC.

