#### **6.1.4.1.3. Intra-patient Dose Escalation**

In the Phase 1b part of the study, patients who have been on study for at least 8 weeks may have their maintenance dose escalated to a higher dose level that has been previously demonstrated to be safe in this study, at the discretion of the Investigator and the CTSC.

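### The protocol contradicts itself on the Hu5F9-G4 dosing interval (weekly or every 2 weeks) and on who approves a change of dose or schedule

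*Protocol*

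**What the plan says.** **Interval, general text.** Protocol section 6.1.1 says "The priming dose will be followed by a weekly maintenance dose" and then "All subsequent maintenance doses of Hu5F9-G4 will be administered at the start of each study week". Neither sentence is restricted to a phase, cohort or cycle. The section opens by referring to Table 1 for Phase 1b and Table 2 for Phase 2.

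**Interval, Phase 2.** Section 3.4 introduces both the planned and the alternate Phase 2 schedules and then says "Starting with Cycle 2, the Day 8 and Day 22 dosing of Hu5F9-G4 has been removed". The synopsis has the same sentence. In Table 2 the current 30 mg/kg schedule is given on Days 1 and 15 from Cycle 2. The alternate 45 mg/kg schedule is given on Days 1, 8, 15 and 22 of Cycle 2 and on Days 1 and 15 only from Cycle 3. Synopsis Table 3 agrees with Table 2, and SAP Table 2 assigns the second KRAS mutant cohort to the 45 mg/kg regimen, weekly in Cycle 2.

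**Interval, Phase 1b.** Table 1 keeps Cohorts 1 to 4 weekly from Cycle 2 with no end.

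**After repriming.** Section 6.1.3 requires a priming dose and "3 weekly maintenance doses prior to starting the Q2W schedule". Section 6.1.4.1 repeats the rule. Neither makes an exception by phase or cohort.

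**Approval.** Under section 3.4, Phase 1b patients with at least 8 weeks on study "may have their dose revised to the RP2DS, at the discretion of the Investigator" (RP2DS: recommended Phase 2 dose and schedule). Under section 6.1.4.1.2, patients with at least 8 weeks of weekly maintenance who stay at the same infusion dose may have the interval "extended to every 2 or 3 weeks, if supported by PK data and approved by the CTSC". Under section 6.1.4.1.3, a higher maintenance dose in Phase 1b is "at the discretion of the Investigator and the CTSC". SAP section 1.1 also names both for a higher dose.

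**The concern.** A site must be able to read one schedule for each patient and one rule for changing it. Here two passages can be followed in good faith and lead to different dosing, or to different oversight of the same change. The text most likely to be used at the point of dosing, section 6.1.1, never mentions the step to every 2 weeks.

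The statistical stake is the meaning of a cohort. Response, PFS and OS are summarised by cohort (SAP section 4), PK per cohort (SAP section 5.1), and safety by actual maintenance dose level (SAP section 6). If dose rate can vary within those groups because of how the text is read, the summaries no longer describe one regimen. The safety grouping cannot reveal this, because it uses mg/kg per infusion and ignores the interval.

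**Working it through.** The documents state no exposure ratio, so there is no figure of the plan's own to reproduce. The check is dose arithmetic from Tables 1 and 2. Dose per 28-day cycle = infusions per cycle × mg/kg. Cumulative dose = 1 mg/kg priming dose + all maintenance doses.

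**(a) Section 6.1.1 against Table 2, 30 mg/kg**
- Cycle 1 is the same under both: 1 + 3 × 30 = 91 mg/kg.
- Each later cycle: weekly 4 × 30 = 120; every 2 weeks 2 × 30 = 60. Ratio 2.0.
- End of Cycle 2, when the first response assessment falls due (section 7.9, Cycle 3 Day 1): 91 + 120 = 211 against 91 + 60 = 151. Ratio 1.40.
- End of Cycle 6: 91 + 5 × 120 = 691 against 91 + 5 × 60 = 391. Ratio 1.77.

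The cumulative ratio approaches 2.0 but does not reach it.

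**(b) Section 3.4 text against Table 2, 45 mg/kg**
- Cycle 1 under both: 1 + 4 × 45 = 181 mg/kg.
- Cycle 2: Table 2 gives 4 × 45 = 180; the section 3.4 sentence gives 2 × 45 = 90. Ratio 2.0 in that cycle.
- End of Cycle 2: 361 against 271. Ratio 1.33.

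**(c) Repriming against the assigned schedule**

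The rule fits the current 30 mg/kg Phase 2 schedule. It does not fit schedules that are still weekly. Once the three weekly doses are done, dose per cycle is:

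| Phase 1b cohort | Table 1 (weekly) | Sections 6.1.3 and 6.1.4.1 (every 2 weeks) |
|---|---|---|
| 1 and 2 | 4 × 10 = 40 | 2 × 10 = 20 |
| 3 | 4 × 20 = 80 | 2 × 20 = 40 |
| 4 | 4 × 30 = 120 | 2 × 30 = 60 |

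A 45 mg/kg patient interrupted before Cycle 3 is likewise sent to every 2 weeks before Table 2 does so. The text does not say where in the calendar such a patient rejoins, so no figure is given.

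**(d) Move of a Phase 1b patient to the RP2DS (30 mg/kg every 2 weeks, 2 × 30 = 60 mg/kg per cycle)**

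| From cohort | mg/kg per infusion | mg/kg per cycle | Section 3.4 | Other provision |
|---|---|---|---|---|
| 1 and 2 | 10 to 30 | 40 to 60 | Investigator | 6.1.4.1.3 and SAP 1.1: Investigator and CTSC |
| 3 | 20 to 30 | 80 to 60 | Investigator | 6.1.4.1.3 and SAP 1.1: Investigator and CTSC |
| 4 | 30 to 30 | 120 to 60 | Investigator | 6.1.4.1.2: PK support and CTSC approval |

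For Cohort 4 the two routes reach the same regimen with different approvers and different clocks. Maintenance starts on Day 8, so 8 weeks of weekly maintenance ends about a week later than 8 weeks on study.

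**Effect on the safety tables.** Cohort 4 on its planned weekly schedule (120 mg/kg per cycle) and Phase 2 patients at 30 mg/kg every 2 weeks (60 mg/kg per cycle) have the same maintenance dose level, so under SAP section 6 they can fall in one column.

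**The case against.** The strongest reply is that a careful reader would rarely go wrong.

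- Section 6.1.1 opens with "Planned Phase 1b dose levels are presented in" Table 1 and sends the reader to Table 2 for Phase 2. Its start-of-week sentence carries a window of 1 day either way and can be read as a visit-timing rule, since Days 1 and 15 also begin study weeks. Several other passages give every 2 weeks from Cycle 2 for 30 mg/kg. This lowers the risk in (a). It does not remove the unqualified weekly sentence just before it.
- In (b), Table 2 sits directly below the text and labels the two schedules. That helps, but the text still introduces both schedules and then states something true of only one.
- In (c), section 6.1.3 gives 30 mg/kg as the maintenance dose, which suggests it was written for that regimen. Section 6.1.4.1 gives the same dose only as an example and also covers Phase 1b, so the rule is not confined to it. A reader might infer that reprimed weekly patients change interval with no approval at all. That goes too far: section 6.1.4.1 requires medical monitor approval to restart after more than 4 weeks. That approval covers the restart, not the change of interval.
- In (d), section 6.1.4.1.2 applies only at an unchanged infusion dose, so it overlaps with Cohort 4 and not with Cohorts 1 to 3. The CTSC itself chose the RP2DS (section 1.5.1.2). No passage says that this choice replaces its role in an individual patient's change.

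A reader might also compare eight 45 mg/kg doses over Cycles 1 and 2 (360 mg/kg) with five after repriming (225 mg/kg). That assumes a reprimed patient would otherwise repeat the whole Cycle 1 and 2 course, including Day 11, which no passage says.

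**Conclusion.** The contradictions are real and should be corrected: following different stated rules gives different dosing, or different oversight, for the same patient. This is an internal inconsistency, not a disputed design choice.

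The size is two-fold in dose per cycle for (a), for Cycle 2 in (b), and for Cohorts 1 to 4 in (c) once the three weekly doses are done. The cumulative difference by the first response assessment is smaller: 1.40-fold at 30 mg/kg and 1.33-fold at 45 mg/kg. Reading dose rate as average steady-state exposure relies on the dose proportionality at 10 mg/kg and above reported in section 1.2.4.2. Cycle 1 is the same under both readings in (a) and (b), and the switch in (d) comes after 8 weeks, so these three do not touch the 4-week DLT period.

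Two stronger readings are not supported. A reader might infer that exposure within a cohort does differ two-fold between sites. The documents hold no site data, and two-fold is a per-cycle figure under a literal reading. A reader might also infer a three-fold dose increase without oversight. Three-fold is per infusion for Cohorts 1 and 2; per cycle it is 40 to 60 mg/kg (1.5-fold), and for Cohort 3 the dose per cycle falls.

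The shared 30 mg/kg safety column arises from the planned schedules alone. The contradictions make it harder to say what that column contains. SAP section 6.1 does report infusions and cumulative dose by cohort, which would show differences in delivered dose but would not separate adverse events by interval.

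**What to change.** The sponsor and CTSC should reconcile protocol sections 3.4, 6.1.1, 6.1.3, 6.1.4.1, 6.1.4.1.2 and 6.1.4.1.3, Tables 1 and 2, the matching synopsis text and table, and SAP section 1.1 with its Table 2. After reconciliation:

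- each cohort has one stated Hu5F9-G4 schedule, and every passage that describes it agrees;
- that schedule includes what follows repriming;
- each type of change (dose, interval, or move to the RP2DS) has one stated approver, one time condition and one evidence requirement.

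Which schedule and which approval rule stand is for the sponsor and CTSC to decide; none is proposed here, and no passage is assumed to prevail.

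SAP section 6 should also say whether patients at the same mg/kg level but different intervals are shown together or apart.

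The cost is wording in the protocol and the SAP. No patients, visits or procedures are added.

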#### **6.1.4.2.2. Infusion Reactions**

Serious infusion reactions requiring medical intervention and immediate, permanent discontinuation of cetuximab included rapid onset of airway obstruction (bronchospasm, stridor, hoarseness), hypotension, shock, loss of consciousness,

myocardial infarction, and/or cardiac arrest. Severe (NCI CTCAE Grades 3 and 4) infusion reactions occurred in 8.4% of 1373 patients receiving cetuximab in 4 different clinical studies, with a fatal outcome in 1 patient (Cetuximab [Erbitux®] Prescribing Information, [Appendix A](#)). Approximately 90% of severe infusion reactions occurred with the first infusion despite premedication with antihistamines.

Patients should be monitored for 1 hour following cetuximab infusion in a setting with resuscitation equipment and other agents necessary to treat anaphylaxis (e.g., epinephrine, corticosteroids, intravenous antihistamines, bronchodilators, and oxygen). If serious infusion reactions occur, study drug administration should be immediately interrupted and permanently discontinued. If hypersensitivity or infusion-related events develop, the infusion rate should be reduced by 50% for NCI CTCAE Grade 1 or 2 and non-serious NCI CTCAE Grade 3 infusion reactions. Patients who experience infusion reactions must be observed until resolution of the event.

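### Section 6.1.1 waives post-infusion monitoring after Cycle 1 for both drugs, Section 6.1.4.2.2 asks for 1 hour after cetuximab in any cycle, and the two conflict on cetuximab-only days

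*Protocol*

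**What the plan says.** Protocol Section 6.1.1 sets the general rule: "All patients should be monitored for at least 1 hour post-infusion for the first 4 weeks". The clock starts after the last drug given that day, so the rule covers both drugs. The section then adds: "Post-infusion monitoring is not required for doses after Cycle 1". It names no drug and makes no exception. Its cetuximab paragraph ends with a pointer to Section 6.1.4.2.

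Within that section, 6.1.4.2.2 says: "Patients should be monitored for 1 hour following cetuximab infusion in a setting with resuscitation equipment". No cycle limit is attached. On the timing of severe cetuximab reactions it reports: "Approximately 90% of severe infusion reactions occurred with the first infusion despite premedication with antihistamines".

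On days with both drugs, 6.1.1 fixes the order and the gap: "Hu5F9-G4 will be administered at least 1 hour after the completion of cetuximab administration".

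Cetuximab is weekly in every cycle, but Hu5F9-G4 is not. Section 3.4 says of Phase 2: "Starting with Cycle 2, the Day 8 and Day 22 dosing of Hu5F9-G4 has been removed, compared with the Phase 1b schedule". Protocol Table 2 and SAP Table 2 show that the 45 mg/kg regimen stays weekly through Cycle 2 and moves to every 2 weeks from Cycle 3.

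Section 6.1.3 covers repriming, including this case: "Patients who experience an interruption of >4 weeks after receiving at least 1 maintenance dose". It restores the 1 mg/kg dose, the 3-hour infusion and premedication for the repriming dose and the next maintenance dose. It also adds a predose antidrug-antibody sample, and laboratory, smear, vital-sign and physical checks at the supplemental weekly visits. It does not mention an observation period.

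**The concern.** A site planning a cetuximab-only visit in, say, Cycle 3 has two instructions. The main dosing section requires no monitoring, and the cetuximab safety section asks for an hour with resuscitation equipment at hand. The waiver does not forbid monitoring, but it lets a site skip the hour and remain within 6.1.1. Mandatory cetuximab premedication covers only the first dose (Section 6.1.2), so at these later visits both premedication and, under 6.1.1, observation become optional.

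Patient protection and uniform practice across sites are at stake. No endpoint, sample size, error rate or dose-escalation decision depends on this.

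**Working it through.** The plan gives no figure on this point to reproduce. The check compares the dosing schedules, then bounds the risk and counts days for repriming.

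**Step 1. Where the two rules differ.** On a dual-drug day Hu5F9-G4 starts at least 1 hour after cetuximab ends. If the patient stays in the clinic between infusions, the cetuximab hour is met before Hu5F9-G4 begins. The rules can differ only when cetuximab is given alone. Scheduled days come from Protocol Tables 1 and 2:

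| Regimen | Cycle | Cetuximab days | Hu5F9-G4 days | Cetuximab only |
|---|---|---|---|---|
| Phase 2, 30 mg/kg | 2+ | 1, 8, 15, 22 | 1, 15 | 8, 22 (2 of 4) |
| 45 mg/kg (Phase 2 and Phase 1b Cohort 5) | 2 | 1, 8, 15, 22 | 1, 8, 15, 22 | none (0 of 4) |
| 45 mg/kg (same) | 3+ | 1, 8, 15, 22 | 1, 15 | 8, 22 (2 of 4) |
| Phase 1b Cohorts 1-4 | 2+ | 1, 8, 15, 22 | 1, 8, 15, 22 | none |

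In Cycle 1 cetuximab is given on Days 8, 15 and 22, always with Hu5F9-G4 and always inside the monitored 4 weeks.

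Cetuximab infusions through Cycle 4: 3 + 4 + 4 + 4 = 15. Cetuximab-only infusions among them:
- Phase 2, 30 mg/kg: 0 + 2 + 2 + 2 = 6 of 15.
- 45 mg/kg: 0 + 0 + 2 + 2 = 4 of 15.

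Unscheduled cetuximab-only visits also arise when Hu5F9-G4 is withheld for toxicity (6.1.4.1), stopped, or extended to every 2 or 3 weeks (6.1.4.1.2) while cetuximab continues. Patients in Cohorts 1-4 are affected only through such changes, including a move to the Phase 2 schedule after 8 weeks (3.4).

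**Step 2. Ceiling on events.** Section 6.1.4.2.2 gives severe infusion reactions in 8.4% of 1373 cetuximab patients, about 90% of them at the first infusion, which leaves about 10% later.

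0.084 × 0.10 = 0.0084, or about 0.8% of patients.

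For the 88 planned Phase 2 patients: 88 × 0.0084 = 0.74, less than one expected patient.

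This is a ceiling for the affected visits. It includes reactions that start during an infusion, which staff would see anyway, as well as the monitored Day 15 and Day 22 infusions of Cycle 1 and all dual-drug days. The documents do not split reactions by onset during or after infusion, so the share that an extra hour would catch is unknown, but it is smaller than this. The figure also ignores prior anti-EGFR exposure in the KRAS wild-type arm and the hypersensitivity exclusion.

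**Step 3. Repriming after a maintenance dose.** The first maintenance dose is on Day 8, and the gap must exceed 28 days.

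Earliest repriming: 8 + 29 = Day 37. If the bar on delays in the first 28 days (6.1.4.1) is respected, the last Cycle 1 dose is on Day 22, and 22 + 29 = Day 51. Both fall after Day 28, so the waiver covers the repriming dose and the maintenance dose after it. Repriming after the priming dose alone would require a delay in Cycle 1, which 6.1.4.1 bars, so it is left out. The documents give no repriming frequency and no event rate after repriming.

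**The case against.** The best defence is that the sections can be read together. Section 6.1.1 sends the reader to 6.1.4.2 for cetuximab details, and a specific rule reached by an explicit pointer is naturally taken to govern. Not requiring something and advising it are also not strictly contradictory. This softens the conflict without removing it: no precedence is stated, and the waiver is worded to cover every dose.

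Other safeguards remain. Vital signs are taken within 30 minutes after each infusion, and serious cetuximab reactions lead to permanent discontinuation. Restarting Hu5F9-G4 after more than 4 weeks needs medical monitor approval. None of these is an hour's observation. Section 1.2.4.1 reports few drug-related toxicities beyond Cycle 1, but for Hu5F9-G4. That supports a waiver for Hu5F9-G4 maintenance doses, which the fix keeps.

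It is also fair that consistency could be restored the other way, by stating a deliberate Cycle 1 limit on cetuximab observation in both sections.

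The documents do not support several stronger readings that a reader might infer:
- That all cetuximab infusions after Cycle 1 lose their observation hour. Dual-drug days keep it through the gap.
- That every 30 mg/kg patient is affected from Cycle 2. Phase 1b Cohort 4 is also 30 mg/kg, but Hu5F9-G4 stays weekly there.
- That 0.8% of patients face an unobserved severe reaction. For the reasons in the working, the figure is only a ceiling.
- That repriming is a second contradiction. No two provisions conflict there. The Amendment 3 summary ties repriming to acute anemia, which Section 1.2.4.1 describes as developing over 1 to 2 weeks. An hour's observation would not detect that, whereas the added weekly checks in 6.1.3 address it.

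**Conclusion.** The inconsistency is real but narrow. For scheduled cetuximab-only visits after Cycle 1 (2 of 4 infusions per cycle once Hu5F9-G4 is every 2 weeks), and for unscheduled ones, 6.1.1 requires no monitoring and 6.1.4.2.2 asks for an hour. Phase 1b Cohorts 1-4 have no scheduled visits of this kind. The expected number of events is small, below about 0.8% of patients. That bound takes the protocol's approximate 90% at face value and assumes that the 8.4% from the four cited cetuximab studies carries over. The case for a change is consistent instructions at low cost; no excess of events has been shown.

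Repriming after a maintenance dose always falls under the waiver. Adding observation there is a reasonable precaution for the sponsor to consider, but it is not the correction of an error.

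**What to change.** In Section 6.1.1, limit the waiver to Hu5F9-G4 maintenance doses. State that the 1-hour cetuximab observation in 6.1.4.2.2 applies in all cycles, and that on dual-drug days the gap of at least 1 hour before Hu5F9-G4 fulfils it. If the sponsor does intend to limit cetuximab observation to Cycle 1, both sections should say so and give the reason.

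The change adds no visits or samples. It costs 1 hour of chair time per cetuximab-only visit, which is 2 hours per patient per 28-day cycle once Hu5F9-G4 is every 2 weeks, or 6 hours (Phase 2, 30 mg/kg) and 4 hours (45 mg/kg) through Cycle 4. Section 6.1.4.2.2 already asks for this time.

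Optional: in Section 6.1.3, add 1 hour of observation after the repriming dose and after the first maintenance dose that follows, the same two doses that already need premedication. The waiver in 6.1.1 would then need to exclude those two doses. This costs 2 hours per repriming.
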